Shipment of Biomarker Samples:

1. Samples need to be shipped to the biomarker core laboratory in the freezer boxes packed into a Styrofoam shipping box containing dry ice. Use an overnight carrier with overnight delivery. Do not allow samples to thaw under any circumstances! Please ship on a Monday-Wednesday. Do not ship on a Thursday, Friday, Saturday or Sunday to be sure there is someone to receive the samples when they arrive.
2. Shipping address:
Attn: [name]. / ASTROH Study
Research Operations Manager
Clinical Trials Unit
University of Louisville
[name]
[name]
T:[contact]
F:[contact] or [name]
[contact]
3. After receiving the shipment, the Styrofoam boxes will be immediately transferred to a -70°C freezer. Samples will be inventoried appropriately (Origin, type of sample, number of aliquots, sample Id number, location within the box and the freezer).
4. Samples will be kept at -70°C until ready to be assayed.

Plasma and CSF from all patients at all time points will be processed by the Core Biomarker Laboratory in a single batch fashion for all biomarkers being tested (except hs-CRP which will be performed at the local site clinical labs). This data will be associated with each patient's study ID# and time of collection. Biomarker lab personnel will remain blinded to treatment allocation. Unused specimens will be stored in a bio repository at the University of Louisville laboratory for up to 10 years after the completion of the study for potential future biomarker analysis without the need for additional informed consent or notification of study subjects at the discretion of the study leadership. Permission for the possibility of future genetic testing on the blood or plasma samples is included in the standard ASTROH informed consent document template provided to each study site.

Biomarker Assays:

A. CYTOKINES (IL-6, TNF α)

1. Plasma or CSF aliquots will be thawed, centrifuged at 10,000 x g for 5 minutes and the supernatants used to measure the concentrations of IL-6 and TNF α using Milliplex MAP Multiplex kits (EMD Millipore, Billerica, MA) according to the manufacturer's instructions. Samples will be assayed in duplicates.

B. ADHESION MOLECULES (sICAM1, P-SELECTIN)

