In addition, the T_{max} per 24-hour period will be documented in the study CRF/Database as well as the number of temperature values recorded as a fever ($>38.3^{\circ}\text{C}$) per 24 hour period. **For the purposes of this study, a day will run from 7 AM until 6:59 AM the following morning.**

Daily T_{max} , Daily Fever Burden, and # of fevers per day will be evaluated as an outcome measure on enrollment day # 2, 4, 6, and 10 to determine any correlation between fever and individual inflammatory biomarker levels and neurological assessments and MoCA scoring at each time point (# 6 and 10). Also, the mean of each subject's average hospitalization daily fever burden (up to 21 days) will be analyzed in relation to the mean of the biomarker levels summed over enrollment days #2, 4, 6, and 10 per study treatment group. Finally, presence of any temperature $> 38.3^{\circ}\text{C}$ and multiple febrile episodes (>2) for a study subjects will be noted and compared between treatment groups as an analysis of categorical proportions.

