15. APPENDICES

15.1 Schedule of Events

	0-48 Hrs Post Ictus	2-12 hrs Post Coiling	Upon initial Enrollment (Enrollment Day 0, 1/12 Hrs post-coiling)	Enrollment Day 0.2 (12 hours post Day 0.1)	Enrollment Day 1	Enrollment Day 2	Enrollment Day 3	Enrollment Day 4	Enrollment Day 5	Enrollment Day 6	Enrollment Day 7	Enrollment Day 8	Enrollment Day 9	Enrollment Day 10	Enrollment Day 11	Enrollment Day 12	Enrollment Day 13	Enrollment Day 14	Discharge	90 Day Follow-up	1 Year Follow-up
Review	X*	X*																			
Informed Consent	X*	X*																			
Randomization		X																			
Demographic Data	X*		X*																		
Medical History	X*		X*																		
Baseline Labs	SOC*		SOC*																		
CBC (with platelet)	SOC*		SOC*		SOC	SOC	SOC	SOC	SOC	SOC	SOC	SOC	SOC	SOC	SOC	SOC	SOC	SOC			
Anti-Xa			RES							RES ^D											
hsCRP			RES			RES		RES		RES				RES							
processing for Serum & CSF Biomarker Analysis			X			X		X ^A		X ^A				X ^A							
Sample shipment																			X ^B		
CT	SOC	SOC																	SOC		
Angiography	SOC								SOC**	SOC**	SOC**	SOC**	SOC**	SOC**							
Coiling Procedure	SOC																				
Send Images to Core			X																X		
Administration ^C			X		X	X	X	X	X	X	X	X	X	X	X	X	X	X			
aPTT ^C	SOC*		SOC*		RES	RES	RES	RES	RES	RES	RES	RES	RES	RES	RES	RES	RES	RES			
Monitor aPTT/Adjust Dosage ^C				X	X	X	X	X	X	X	X	X	X	X	X	X	X	X			
WFNS SAH Scale	X	X																	X	X	
Glasgow Coma Scale	X	X								X				X					X	X	
NIH Stroke Scale	X	X								X				X					X	X	
MoCA			X							X				X					X	X	
Modified Rankin Scale	X***																		X	X	
Return to Work																			X	X	
QOLIBRI-OS																			X	X	
Barthel Index																			X	X	
Trail Making Tests																			X	X	
Lawton-IADL																			X	X	
CES-D																			X	X	
CIS-F																			X	X	

* Not duplicated, can be performed at either time point

** Any of these time points would be acceptable to satisfy this requirement, these are not duplicates of the angiography test but represent ONE angiography over this range of dates

*** Historical mRS

^A: Baseline and day# 2 biomarkers should be drawn on exact date. Day 4, 6 and 10 should be drawn as close as possible to the exact date, but may have +/-24 hours to accommodate for lab processing schedule

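### The aggregate fever–biomarker analysis in Section 6.12.6 sets a hospital-stay fever average of up to 21 days against biomarker levels summed over days 2 to 10, and its fever window conflicts with the infusion-period window in the same section

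*Protocol*

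**What the plan says.** Protocol Section 6.12.6 defines daily fever burden and says it is calculated for the period of the study drug infusion. Sections 6.8 and 6.13 put that period at 14 days at most, and secondary objective 8 in Section 1.2.2 also refers to the infusion.

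The end of Section 6.12.6 then plans two analyses:

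- Per day: daily Tmax, fever burden and fever count are "evaluated as an outcome measure on enrollment day # 2, 4, 6, and 10 to determine any correlation" with biomarker levels and clinical assessments. For this purpose "a day will run from 7 AM until 6:59 AM the following morning".
- Aggregate: each patient's fever burden per day, averaged across the hospital stay to a limit of 21 days, is set against a biomarker quantity described as "the mean of the biomarker levels summed over enrollment days #2, 4, 6, and 10 per study treatment group".

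On sampling, Section 6.11 takes CSF only when a drain is in place. Footnote A to the Schedule of Events (Section 15.1) says "Baseline and day# 2 biomarkers should be drawn on exact date", and then "Day 4, 6 and 10 should be drawn as close as possible to the exact date, but may have +/-24 hours". Stored samples carry the date and time of collection, and the core laboratory results are linked to the "study ID# and time of collection".

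**The concern.** The aggregate analysis asks whether patients with more inflammation have more fever. As worded, its two sides cover different periods and respond differently to events that have nothing to do with that question.

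- Fever from day 11 onward counts on the fever side and has no biomarker counterpart.
- The fever average is divided by the days in hospital, so two patients with the same fever course differ if one stays longer.
- A sum over four draws drops when a draw is missing. For CSF, missing draws follow from drain removal, so the sum partly measures how long a drain stayed in.

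Length of stay and drain duration could therefore produce, hide or distort an association. The section also gives two fever windows, so two analysts following it could compute different fever averages for the same patient. Section 6.12.6 ties the inflammation hypothesis closely to fever, so the result would probably be cited for mechanism even though it is exploratory.

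**Working it through.** **1. The windows side by side (Section 6.12.6).** The fever average runs over hospitalization, up to 21 days. The fever-burden calculation runs over the infusion, up to 14 days. The biomarker levels come from days 2, 4, 6 and 10. Days after the last biomarker draw make up (21 − 10)/21 = 52% of a 21-day fever window and (14 − 10)/14 = 29% of a 14-day window.

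**2. Dependence on stay.** Assume one fever course: 20 °C·h per day for 7 days, then 2 per day.

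- 14-day stay: (7×20 + 7×2)/14 = 154/14 = 11.0.
- 21-day stay: (7×20 + 14×2)/21 = 168/21 = 8.0.
- Days 2–10 only, either stay: (6×20 + 3×2)/9 = 126/9 = 14.0.

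The first two differ only through length of stay, and a common window removes the difference. The profile is an assumption. Some dependence arises whenever late fever differs from early fever.

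**3. Dependence on missed draws.** Take four equal levels L. The sum is 4L with all draws, 3L with one missed (25% lower), and 2L if a CSF drain is out after day 4 (50% lower). The mean of available levels stays at L throughout.

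**4. Possible attenuation.** The protocol gives no detectable correlation for fever against biomarkers, so the figures in Section 10.2 serve only as a yardstick. They reproduce with the Fisher z formula, one-sided 5% and 80% power:

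r = tanh[(1.645 + 0.842)/√(n − 3)]

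- n = 80: 0.276, and n = 88: 0.263 (the protocol states 0.27).
- n = 44: 0.370 (the protocol states 0.37 within an arm).

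Now let fever and biomarkers follow one day-level process with correlation c + (1 − c)ρ^|i−j| between days i and j, where c is the stable between-patient share and ρ the day-to-day autocorrelation. Compare the biomarker mean on days 2, 4, 6 and 10 with the fever mean on days 1–21, and then with the fever mean on days 2–10.

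- ρ = 0.5, c = 0: 0.642 against 0.870, ratio 0.74.
- ρ = 0.9, c = 0: 0.851 against 0.985, ratio 0.86.
- ρ = 0.5, c = 0.6: 0.945 against 0.978, ratio 0.97.

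Over ρ = 0.5–0.9 and c = 0–0.6 the ratio runs from 0.74 to 0.97. Applied to r = 0.27 with n = 80, power goes from 78% to between 55% and 76%. With a fever window of days 1–14, the first case gives 0.795/0.870 = 0.91. These runs assume complete draws and the same stay for everyone, so they leave out the effects in steps 2 and 3.

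**5. Off-day draws.** The ±24 h allowance covers days 4, 6 and 10, not baseline or day 2. In the extracted schedule the footnote mark sits on the stored-sample row and not on the hs-CRP row, although the table is damaged and this reading is tentative. A recorded draw time and the 7 AM definition together give exactly one study day: a 5 AM draw on the calendar date of day 4 belongs to the study day that began on day 3. The data needed for matching are therefore held, but the protocol states no matching rule.

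**The case against.** **Stronger readings that a reader might infer.** One is that the per-day analysis pairs values by nominal day, so that it correlates values from different times and loses much of its power. The documents do not support this. Section 6.12.6 gives no pairing rule for an off-day draw, collection times are recorded for the stored samples, and such a rule may sit in an analysis plan that is not shown. The 7 AM day is a definition, not an error. The 5 AM example is a mismatch only if draws are dated by calendar day and fever by study day.

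A figure for the loss can be produced: with one third to two thirds of draws a day off and autocorrelation 0.3–0.7, r = 0.37 falls to 0.20–0.33 and power at n = 44 to 36–72%. With 10–50% off and autocorrelation 0.5–0.9, r = 0.27 becomes 0.20–0.27 and power at n = 80 is 56–78%. None of these inputs is in the protocol, which asks for draws as near the exact date as possible. Nor is the 24 hours before a draw clearly the right window, since the section describes cytokine release as a cause of fever.

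A second inference is that the aggregate sentence leaves only two group means, from which no correlation can be estimated. That is strained: the sentence speaks of each subject's average, and the closing phrase most naturally means by arm.

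**Other objections.** The summed levels might be meant to be divided by their number, and missing-data handling commonly belongs in an analysis plan. Fever–biomarker correlation is not among the listed objectives or endpoints, and fever is compared directly between arms.

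**What stands.** These points limit importance. They do not remove the two fever windows, the unequal spans or the word summed, all of which the protocol itself fixes.

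**Conclusion.** The point holds for the aggregate analysis. Followed as written, it gives late fever no counterpart, makes the fever average depend on stay, and makes the biomarker total depend on the number of draws. The conflict between the infusion-period and hospitalization windows needs no assumption. The direction of the missed-draw effect on a raw sum is certain, and 25% per missed draw assumes four similar levels. The stay effect (11.0 against 8.0) and the attenuation factor (0.74–0.97) rest on assumed profiles and correlations. They are illustrations, because the protocol does not allow the real loss to be derived.

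For the per-day analysis the finding goes no further than this: a one-line matching rule would be useful, and no error is shown. The matter is exploratory and does not touch the primary endpoint, the sample size or the safety analyses.

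**What to change.** In Section 6.12.6:

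1. Reconcile the two fever windows. State one period for the fever-burden calculation, say which days it means for controls, who receive no infusion, and say where a different period is intended.
2. Rewrite the aggregate analysis with patient-level values, analysed by arm, over a common window. For example, use mean daily fever burden on days 2–10 against the mean or time-weighted mean of the available biomarker levels on days 2–10, in place of the sum. Days 2–10 lie within both the 14-day and the 21-day limits, so this can be settled separately from item 1.
3. For stored plasma and CSF samples drawn off the nominal day, match to the study day (7 AM to 6:59 AM) that contains the recorded draw time. Section 6.11 documents hs-CRP by time point, so the rule extends to it only if its draw time is also captured.

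The cost is wording and programming, since temperature logs and stored-sample times are already collected. Two limits remain. Late fever drops out of this one analysis, though it can still be reported descriptively. A mean of available levels removes the effect of the number of draws but still depends on which days were sampled, so the number of CSF draws per patient should be reported beside it.

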6.12.7 Blood Transfusions

We recommend that transfusion of packed red blood cells be avoided unless the patient has **symptomatic** anemia. Transfusion of packed red blood cells has been reported to be associated with decreased cognitive outcomes in patients following aSAH. Should a transfusion of packed red blood cells be necessary per a site's SOC, it will be recorded in the subjects' CRFs. All transfusions of other blood products will also be recorded in the CRFs. Please keep in mind that **if blood transfusions are given during a bleeding event, administration of 2 or more units will automatically designate that bleeding event as a Major bleeding event.** See section 8.5 for more information.

Recommendations based on the Neurocritical Care Society Consensus paper:

- Measures should be taken to minimize blood loss from blood drawing.
- Transfusion criteria for general medical patients should not be applied to decisions in SAH patients.
- Consider RBC transfusions to maintain hemoglobin above 8 g/dl, but for purposes of this study please only transfuse 1 unit of packed red blood cells when there is no urgent bleeding event and then reassess before additional transfusion.

6.12.8 Nimodipine

Nimodipine will be given to subjects at 60 mg by mouth every 4 hours per the SOC at each site (capsule or liquid suspension). However, reduction in dose with increased frequency of dosing to 30mg by mouth every 2 hours is sometimes utilized for patients who have serious hypotensive responses to the 60 mg dose, and is an acceptable alternative in this study. Holding Nimodipine will be done as per the SOC at each clinical site, and is usually only done in the setting of severe hypotension not responsive to mild to moderate pressors. However, whenever possible, the clinical team should avoid holding nimodipine. If nimodipine is held for severe hypotension, it should be resumed as soon as the blood pressure is corrected and inotropic medications are available to help support the blood pressure. Decreasing the total daily dose of nimodipine to less than 360 mg / day or discontinuing nimodipine should be avoided, although this eventuality will be up to the discretion of the treating physician. Nimodipine compliance will be recorded in the EDC for this study. Experience in the LDIVH post-craniotomy study suggested that co-administration of LDIVH and nimodipine may yield the best clinical results. Great care should be taken when using nimodipine in the setting of severe aSAH induced cardiac dysfunction as this could potentiate a serious hypotensive event not easily correctable with vasopressor medications.

6.12.9 Statins

Statin medications have previously been suggested to help reduce the incidence of delayed cerebral ischemia and improve outcomes in aSAH patients. However a recent meta-analysis (Vergouwen MD, et al. *J Cereb Blood Flow Metab.* 2009;29:1444-1453) showed no clinical benefit and a more recent large phase III placebo controlled trial comparing 391 patients receiving 40 mg simvastatin daily versus 412 patients receiving placebo showed no benefit in outcomes as measured by ordinal mRS analysis adjusted for admission WFNS grade (Kirkpatrick PJ et al. *Lancet Neurol.* 2014;13(7):666-675). Therefore, for purposes of this study, statin agents should not be newly initiated for aSAH study subjects. If the study subjects have previously been taking statins for other medical problems then they may continue at the previous dosing and schedule. Any statin usage in this case will be recorded in the EDC.

6.12.10 Magnesium sulfate

Magnesium sulfate has also previously been suggested to help improve outcomes after aneurysmal subarachnoid hemorrhage. Recent randomized placebo-controlled multicenter phase III trials (IMASH and MASH-2) have not demonstrated any benefit (Wong GK et al. [IMASH] *Stroke* 2010;41:921-926 and Mees SMD et al [MASH-2] *Lancet* 2012;380(9836):44-49). Therefore, for purposes of this study, magnesium sulfate infusion should not be given routinely as a prophylactic neuroprotective agent. It is acceptable to give magnesium sulfate to patients who have low magnesium levels for routine electrolyte replacement.

6.12.11 Corticosteroids

Corticosteroids with predominant glucocorticoid effect should be avoided. Symptomatic treatment of headaches or other inflammatory or meningismus related symptoms should be avoided. Steroid medications should only be used as required for stress dosing or to treat hypocortisolism. Corticosteroids with predominant mineralcorticoid effect (such as fludrocortisone / Florinef for treatment of natriuresis / hyponatremia) are acceptable. Chronic corticosteroid usage prior to admission is considered a criteria for exclusion to enrollment.

6.13 Completion Of Study Drug Infusion

The study drug infusion will be stopped after completion of 14 full days of infusion. In the unlikely event that the patient is discharged home or to a facility prior to this time point, then the study drug infusion will be stopped at least two hours immediately prior to discharge. After stopping the study drug infusion, all previous restrictions placed on the patients during the study drug infusion time period as listed in this protocol will no longer be in effect.

6.14 Post-Infusion (Pre-Discharge) Head CT

A post-infusion head CT is required by this protocol. Most centers will perform a head CT during the later phases of the acute admission to evaluate for development of delayed hydrocephalus and / or to obtain a baseline scan prior to discharge. As a result, this scan will be considered part of the SOC and will not be funded by the study. We prefer the timing of this scan to be 12 hours (\pm 12 hrs) after completion of the study drug infusion (or an equivalent time period in the control group) to allow for comparisons to the post-procedure (pre-enrollment) head CT. If the patient's hospital discharge is planned for a time period < 24 hours after the cessation of the study drug infusion, the CT scan should be obtained prior to discharge.

6.15 Imaging Processing Procedures

A study imaging processing company will be used to systematize the redaction of protected health information and confirm image quality prior to image review by the

imaging core lab. OCULUS Imaging, Inc. under the direction of [name], an interventional neuroradiologist, Knoxville, Tennessee will provide the imaging database for the study (<https://www.oculusimaging.com>). The OCULUS imaging system is a secure HIPAA compliant system that has been used in numerous clinical trials for processing of images for imaging core lab review. Radiologists with the imaging core lab would be able to remotely log into the OCULUS imaging system to review and report on the imaging data preventing the need to mail hard copies (CDs) of the images and making it less likely for an unanticipated disclosure of protected health information.

However, should the OCULUS Imaging system not be utilized or be temporarily disabled, radiological images pertinent to the study will be sent to the Imaging Core Lab for verification of findings. This process would involve mailing CD-ROMs with de-identified images if the electronic imaging processing system is not functioning properly.

For Direct Shipping of Imaging CD-ROMs [In the event of an unlikely long-term failure of Oculus Imaging]: Shipping address:

ASTROH Imaging Core Lab
Attention: [name]
Cerebrovascular Center
[name]
[name]

Email: [contact]

DICOM digital copies of these images will be maintained by the Imaging Core Lab or by OCULUS Imaging, Inc. for a minimum of 10 years after study completion. The storage of these images and any related data will be HIPAA compliant. The images will be labeled with the patient's assigned Study Identification Code, the date of imaging (Day # from enrollment), and type of imaging. Whenever possible these images will be in a de-identified form, however, some images have patient identifiers that may not be able to be removed. All images will be shared and disposed of in a secure manner and the collection, sharing, and storage of these images will be disclosed in the informed consent document and HIPAA Authorization. [name] will supervise the Imaging Core Laboratory procedures and will have direct access to the Oculus Imaging Database.

6.16 Clinical Assessments Through Post-Enrollment Day #14

Study personnel at each site will be trained in the proper clinical assessments of study subjects. The team members performing the inpatient clinical assessments will NOT be allowed to perform the blinded clinical assessments at the 90-day or 1-year follow-up visit.

Study specific clinical assessments of study subjects will occur on post-enrollment day, day 6, and day 10 during the acute hospitalization.

- **Glasgow coma scale score (GCS) [5 minutes]**
- **NIH Stroke Scale (NIHSS) [10 minutes]**
- **Montreal Cognitive Assessment (MoCA) [15 minutes]**
 - This MoCA has three English versions. A different English version should be given to study subjects during each time point (Version 1: Enrollment; Version 2: post-enrollment day #6; and Version 3: post-enrollment day #10) [Note: The final MoCA assessment on the 90-day follow-up visit will be Version 1 (repeated) and MoCA assessment on the 1-year follow-up will be Version 2 (repeated)]
 - Similarly, there are other language options with three versions (i.e., Dutch, German, Portuguese, and Spanish). An identical version test distribution would be used in these other languages. Test information and other languages are available at www.mocatest.org)
 - **The administration of the MoCA at enrollment should be done at least 12 hours after removal of the endotracheal tube and recovery from any anesthesia given during the coiling procedure.** This may require that the MoCA to be administered on post-enrollment day #1 instead of on the enrollment day (post-enrollment day #0). This rule is in place to minimize post-anesthesia effects from influencing the MoCA score. In the event that the patient remains intubated past post-enrollment day 1, the MoCA test should be performed as soon as possible after extubation, once sedation has cleared.
 - **MoCA assessments will be audio recorded in order to verify accurate scoring. Recordings will be labeled with subject ID number only and destroyed at the end of the study.**

